Within O&G, at Certificate of Completion of Training (CCT), there is concern that trainees lack the confidence and skills to perform the same breadth of procedures as the previous generation.³ An intra deanery survey showed that 67% of O&G trainees felt inadequately prepared for CCT⁸. In 2012, analysis of 155 successful applications for CCT in general surgery (GS) revealed that only 67% of the cohort had achieved the logbook requirement of 1600 cases and around 73% had the necessary experience in index procedures.⁹ There is currently no literature to highlight expectations and opinions of consultants or programme directors of trainees' skills within GS or O&G in the UK, which we believe to be one of the indicator of training standards.

Whilst the requirements for CCT for general operative skills in open and laparoscopic surgery are comparable in both specialties, the training pathways defer significantly. GS training is 8 years in duration (CT1, CT2, ST3-ST8), whereas O&G consists of 7 years of specialty training (ST1–ST7). The ST1-ST5 years in O&G is mainly devoted to obstetrics and only those trainees pursuing a gynaecological training pathway undertake an intensive period of surgical training in the last two years of their training. We believe there is also earlier exposure to laparoscopy in GS training with a greater volume of laparoscopic work in comparison to O&G training. To our knowledge, there is no direct comparison of O&G and GS training pathways and outcomes in laparoscopic skills.

It is known that greater exposure to laparoscopic training is associated with “muscle memory” and may contribute to reducing physical and mental stress of the surgeon. It is not known whether the existing training is sufficient to meet the demands of a laparoscopic gynaecological or GS consultant or whether the differences in training affects the development of fundamental laparoscopic skills (FLS). These FLS include spatial awareness, hand eye co-ordination, bimanual dexterity and laparoscopic suturing. We would expect trainees to be better at FLS with more laparoscopic surgery exposure. The measurement of muscular and cognitive

fatigue can be regarded as a surrogate marker of exposure to laparoscopy giving further insights into the quality of laparoscopic training between the two training programs.

Hypothesis

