Personal details from these questionnaires will be separated and a study number will be allocated to both parts of questionnaires. The same study number will be written on the trainee's badge as this number will be

used for filling out the evaluation sheets. A single sheet of paper will allow us to recognise the study number against relevant trainee in case we need to contact them at a later point. This form will be securely stored in a locked cabinet in an NHS locked office accessible only to the research team.

There are four FLS tasks and they are carried out using validated training models called LASTT (Laparoscopic Skills Training and Testing method) and SUTT-1 (Suturing and knot tying Training and Testing method). LASTT is a wooden model and SUTT-1 is a foam sponge.

A sub selection of trainees will be randomly chosen on the day (with their consent) to have EMG and EEG monitoring whilst performing these tasks.

A summary of the tasks is given below in table 1 below followed by a more detailed explanation later in this section.

Table 1: Summary of FLS tasks.

Task	Task Aim	Ideal time for completion	Data to be recorded*
1	Camera navigation to find 14 targets – repeated 3 times	Ideal time for completion of task 1 is 2 minutes and 30 seconds. For trainees unable to achieve the ideal target time can continue up to a maximum of 5 minutes.	Time taken (min/sec) to find 14 targets if within 5 minutes. If trainee exceeds 5 minutes then we will record last target found. Penalty- subtracting 1 target from the total found targets if ideal time of 2:30 is exceeded.
2	Transfer 6 objects (repeated 3 times)	Ideal time for completion of task 2 is 3 minutes	Time taken (min/sec) No of objects dropped
3	Position 6 objects (repeated 3 times)	Ideal time for completion of task 3 is 3 minutes	Time taken (min/sec) No of objects dropped
4	Perform 4 interrupted sutures and 4 knots. (done once only)	Maximum time allowed is 15 minutes	Time taken (min/sec) Quality of the sutures and knots***

***The quality of the sutures and knots will be assessed after the completion of the task by 2 independent assessors using validated tools.¹⁰

EMG and EEG readings will be recorded on a subsection of trainees whilst performing the laparoscopic tasks - 4 GS trainees at grade ST3/ST4/ST5, 4 trainees at ST7/8 from GS and, likewise, 4 O&G trainees at ST3/ST4/ST5 and 4 trainees at ST6/7 from O&G.

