Trainees will be expected to place interrupted sutures between two dots and perform 4 intra corporeal knots with 3 throws. They will be instructed to place sutures between the two dots along the first 4 rows on the foam pad. The trainee is not expected to use the 5th row at the bottom of the foam pad. A total of 15 minutes will be allowed for this task and the time taken to complete 4 sutures and 4 knots if performed will be recorded. If the trainee runs out of time, then total number of sutures +/- knots performed within the 15 minutes will be recorded. At the completion of the tasks, each foam pad will be labelled with the trainee's study number and collected. The quality of suturing and knot will be assessed after completion of the task using validated SUTT scoring system by two independent assessors **(Appendix 9)**.

Measurement of EMG and EEG

Musculoskeletal and cognitive fatigue will be tested using electromyography (EMG) and electroencephalography (EEG) respectively in a sub set of trainees as described earlier. They will be fitted with EMG and EEG electrodes as per the protocol and this data will be collected for round 2 of tasks 1-3 and throughout the duration of the suturing task 4. As the equipment is wireless, it is anticipated that the trainee's freedom of movement will not be affected by it. EMG will be measured by placing wireless electrodes over arms, neck and upper and lower back muscles **(Appendix 10)** and EEG will be recorded using wireless electrodes over the scalp using a validated protocol **(Appendix 11)**.

Location and timescale for experiments

We have opted to conduct these tasks in a large seminar/conference room to minimise any potential pressure on performance of another colleague. We are restricting the number of trainees to a maximum number of 6 per each run. We will conduct these tasks over 3 weekends (2 consecutive weekends and one weekend 3 weeks later). The rationale behind this is to increase the chances of recruiting volunteers who may be restricted otherwise by on-call commitments or might be away on leave.

Choice of location will be between Royal Blackburn hospital and Manchester based hospitals.

Outcome measures

The primary outcome measure:

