We believe consent is a dynamic process and it will start when we make initial contact with the trainees and consultants via email. They will be provided with participant information sheet including contact details of the research team. In part 2 consent will be confirmed in writing for both the laparoscopic tasks and EMG/EEG recordings. All efforts will be made to communicate appropriately including facilitating access to translational and interpretation services if needed. All our prospective trainees are likely to be fluent in English so we do not anticipate English language barriers.

Risks, burdens and benefits

The study does not involve any invasive procedures/tasks. It does not raise any issues which may be upsetting to the trainees.

Muscular and cognitive fatigue will be measured using wireless sensors over head, shoulders, arms, upper and lower back. These are painless, discreet and unlikely to impede any freedom of movements.

The researcher responsible for applying these electrodes is a male surgeon. If a female trainee prefers the electrodes to be applied by a female staff then we will respect such wishes. We have trained female members of the research team to be able to undertake this task.

Four laparoscopic tasks are assessed using simulator boxes with inanimate models. Study duration will be kept to a minimum to avoid fatigue and refreshments will be provided throughout.

To minimise pressure on trainees, the study will be conducted over a weekend and away from their workplace. We will try to ensure that there is plenty of physical space for each trainee and their facilitators to minimise performance related pressure on each other. The environment will be kept comfortable and constant to minimise adverse effects on performance. If they want to have a different facilitator because they may know or feel uncomfortable with them then they can discreetly request this from a member of the research team. They don't have to give a reason.

We will try to minimise any burden on trainee by providing the following: Ensuring access to lavatory facilities, refreshments, lunch and in inconvenience allowance aimed at covering their travel and parking costs.

The risk of covid 19 transmission is an on-going issue. We will adhere to local guidelines regarding reducing transmission, wear face covering, maintain a distance and have ample hand sanitising facilities in place. We

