Similar to the EMG data capture, EEG data will also be collected during the surgical task. The skin site on the head will be prepared as previously described before the electrode gel and electrode cap are applied. Electrodes will be placed over the cortex using an 8-channel electrode montage to record ongoing EEG oscillations during surgery. Electrodes will be positioned according to the 10-20 international electrode placement system. The main EEG channels of interest will be positioned over the occipital and parietal cortex, namely electrode locations O1, O2, P3, P4, P7, P8 where maximal alpha activity can be detected. A wireless EEG system has been selected so that it is minimally invasive and does not interfere with movement during the task.

Data will be collected and analysed using Enobio 8 5G (Neuroelectronics, Cambridge, MA, USA) using standard referencing, sampling, filtering and smoothing technique. We will compare peak alpha power, and alpha spindle duration and amplitude between groups. Changes in EEG power spectra, specifically in the alpha frequency band, will be used to monitor alertness. We will also be able to identify how alertness changes over time during surgery through the EEG power spectra.

Figure: Example wireless EEG sensor placement

Appendix 12

Equipment

6 stack systems (monitor, 10mm optic (0 and 30 degrees, light))

Laparoscopic 5mm ports x2, 10mm port x1

Tissue grasping forceps (Johans)

Kelly/Maryland dissecting forceps

Needle holders (right and left)

Laparoscopic scissors

Vicryl 2.0 sutures each one cut to 20cm in length.

SUTT1 foam pads

Wooden LASTT model with its inserts

Stop-watch

Weighing scale

Measuring tape for height

Appendix 13

Assessor Information

An assessor will be allocated to each trainee who will mount the relevant inserts into LASTT model, replace the LASTT model with SUTT suturing pad and set up equipment as in Appendix 9.

They will provide the trainee with standardised instructions before each task and discreetly fill out the scoring sheets. The assessors will not give any performance feedback although they can clarify the instructions as many times as necessary on the trainee's request. They will use the stopwatch and keep the trainee updated with how much time they have used up.

Task 1:

The aim of the first exercise is to navigate the 30° camera to locate all targets in the shortest amount of time.

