Place the LASTT model in the box such that the top edge of this box is lined up with the second white pin along the side of box trainer. Put the inserts as per sequence 1.

A 10mm and 30 degrees camera is used. It is to be inserted through the most proximal central port on the Szabo box trainer. Request the trainee to read the instructions and then show them the demonstration video.

Check trainee's understanding of the task.

On the LASTT model there are 14 targets. Each target consists of a large character and a small character (numbers and alphabet letters).

The task time begins when the trainee inserts the camera to find the first target. The small character on that target indicates their next target.

The first target is always '1a'. Trainee starts their search by locating the first target "1a". The figure below is an example of what the first target looks like.

Large character '1' corresponds to the starting character.

Small character 'a' corresponds to the next character to find which will appear as a large character on the subsequent target.

Once the small character is found, trainee needs to zoom in and place the small character in the circle on the screen. If you approve that the entirety or boundaries of the small character is placed in the circle on the screen then indicate that they can move on to next target by saying 'next.' The trainee should now navigate the camera to find capital 'A' on the next target, then zoom in, find the small character next to it

and place it in the circle on the screen and then move on. The trainee can continue until all 14 characters have been found indicated by finding 'Nend'. This completes the task.

Record the time taken to find 14 targets for each round. Ideal time for completing this task is 2 minutes and 30 seconds. However we are allowing a maximum time of 5 minutes for its completion. If trainee is unable to complete the task within 5 minutes, then stop the trainee at that point and record the last target they found; e.g. Mq.

Now change the inserts for round 2 using sequence 2 and repeat above. Record the same data as above before proceeding to round 3 using sequence 3. Once this round is completed, record the above data and move the trainee on to task 2.

Exercise 2: Hand-eye Coordination

The aim of this exercise is to test the trainee's ability to navigate the camera with their non-dominant hand and to simultaneously handle the forceps with their dominant hand.

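### Does recording EMG and EEG only in round 2 of Tasks 1–3 leave the fatigue comparison without the data it needs?

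*Protocol*

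**What the plan says.** The recording window is fixed in the Protocol under Measurement of EMG and EEG: "this data will be collected for round 2 of tasks 1-3 and throughout the duration of the suturing task 4". Table 1 gives three rounds for each of Tasks 1, 2 and 3 and a single performance of Task 4. Part 2 sets the monitored subset at four trainees in each of the four specialty-by-grade groups, 16 in all.

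The purpose of the signals is given in three places:

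- Objective 2 compares musculoskeletal and cognitive fatigue between O&G and GS trainees.
- Outcome measures lists EMG and EEG signal analysis as a secondary outcome.
- Appendix 11 names the EEG comparison: "We will compare peak alpha power, and alpha spindle duration and amplitude between groups". It then adds: "We will also be able to identify how alertness changes over time during surgery through the EEG power spectra".

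Appendix 10 notes that normalised EMG makes it possible to look at muscle activity at different times, including within one session.

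**The concern.** Fatigue develops over time, so one expects to see early and late measurements of the same activity. Here each of Tasks 1–3 is recorded once, in its middle round. The longest same-task view is one round: at most 5 minutes in Task 1 and 3 minutes in each of Tasks 2 and 3. Comparing across tasks does not help, because Appendix 13 runs Tasks 1 to 4 in a fixed order and time is then confounded with task.

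The Protocol gives no reason for choosing round 2. A later analysis plan can choose windows and models, but it cannot restore signal that was not collected. If a planned analysis needed change across rounds, the loss would be permanent. The trainees perform all nine rounds anyway and the sensors are wireless, so recording the other six rounds seems an easy gain.

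**Working it through.** **Inputs (Protocol).** The limits per round are 5 minutes for Task 1 and 3 minutes each for Tasks 2 and 3, with three rounds each. Task 4 has a 15-minute limit and is done once. For the shorter scenario, Table 1 states "Ideal time for completion of task 1 is 2 minutes and 30 seconds"; its ideal times for Tasks 2 and 3 equal their limits. The monitored subset is 4 × 4 = 16 trainees. The Protocol states no sample size, power or effect size for EMG or EEG, so there is no figure of its own to reproduce.

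**Step 1: how much is recorded.** Maximum recorded time = sum over Tasks 1–3 of (rounds recorded × time per round) + Task 4.

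| | Tasks 1–3, round 2 only | Tasks 1–3, all rounds | With Task 4 (15 min): now | With Task 4: all rounds | Extra per trainee |
|---|---|---|---|---|---|
| At the limits | 5 + 3 + 3 = 11 min | 15 + 9 + 9 = 33 min | 26 min | 48 min | 22 min |
| At the ideal times | 2.5 + 3 + 3 = 8.5 min | 7.5 + 9 + 9 = 25.5 min | 23.5 min | 40.5 min | 17 min |

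Over 16 trainees the extra signal is 16 × 22 = 352 minutes (5.9 hours) or 16 × 17 = 272 minutes (4.5 hours). Only Task 1 differs between the rows, and quicker trainees would give less, so 17 minutes is not a lower bound. The premise is therefore correct: one third of the Task 1–3 time is recorded.

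**Step 2: does the planned comparison need the missing rounds?** Objective 2 and the comparison named in Appendix 11 contrast the specialties. All monitored trainees are recorded in the same round of the same tasks, with the same target sequence and in the same order. Round, sequence and task position are therefore equal in both specialties, and the between-group contrast is matched. No objective or outcome measure asks for a change from round 1 to round 3.

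**Step 3: is the remark about time supported?** Appendix 11 says that changes in alertness can be identified. It does not say that this will be done across rounds of one task. Task 4 is recorded from start to finish, up to 15 minutes, and at the limits it supplies 15 of the 26 recorded minutes. Trends inside each recorded round add to this. The EMG sentence in Appendix 10 describes what normalisation allows and does not commit the study to an analysis.

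**Step 4: what would the extra rounds show?** Appendix 13 ties the sequence to the round: "Now change the inserts for round 2 using sequence 2 and repeat above", then sequence 3 for round 3. Round and sequence are the same factor, so change from round 1 to round 3 within a trainee contains fatigue, practice and sequence together. Comparing that change between specialties would cancel a sequence effect common to both. It would not cancel practice gains that differ by specialty, and the Protocol's background gives a reason to expect such a difference: "We believe there is also earlier exposure to laparoscopy in GS training with a greater volume of laparoscopic work in comparison to O&G training". The summed spans of 15, 9 and 9 minutes would also be three separate bouts with insert changes between them, which allow recovery. They are not comparable with the continuous Task 4 recording. The result would be a descriptive contrast in four trainees per group that does not isolate fatigue.

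**Step 5: is it cheap?** The Protocol states "We are restricting the number of trainees to a maximum number of 6 per each run". With 16 of 40 trainees monitored, a full run would hold 6 × 16/40 = 2.4 monitored trainees on average. Neither Appendices 10 and 11 nor the equipment list in Appendix 12 gives the number of sensor sets. Whether continuous recording is easy cannot be settled from the document.

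**The case for a change.** The strongest case for the concern is that the Protocol itself fixes the data collection, so no analysis plan can repair it. The signals are meant to measure fatigue, and performance in Tasks 1–3 is averaged over three rounds while the physiological measures come from one. The trainees already perform every round, and sensors must in any case be in place by round 2 of Task 1. Recording more adds no task time and does not conflict with the stated aim: "Study duration will be kept to a minimum to avoid fatigue". If full recording were impossible, the sentence on alertness could at least be limited to Task 4 and within-round trends.

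The facts in this case stand: the minutes are right, unrecorded rounds cannot be recovered, and no reason for choosing round 2 is given. They do not make the choice a fault. The Protocol plans no analysis that links the signals to performance round by round, so the differing number of rounds affects no stated result. Narrowing the Appendix 11 sentence would correct nothing untrue, since it already claims no more than the Task 4 recording and the within-round trends can support. How to split Task 4 into early and late windows is a matter for the analysis plan.

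**Conclusion.** The concern does not hold. The restriction is real: 3 of 9 rounds, and at most 11 of 33 minutes, of Tasks 1–3. It leaves the planned between-specialty comparison matched, and the statement on alertness over time is supported by up to 15 minutes of continuous Task 4 recording together with within-round trends. The 17 to 22 extra minutes per trainee would give a contrast confounded with practice and sequence, on a secondary outcome in 16 trainees, and would alter no planned comparison. Recording all rounds is a preference on which investigators may reasonably differ.

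This rests on two readings: that Objective 2 is a comparison of specialties at matched points, and that the sentences on time in Appendices 10 and 11 describe what the signals can show and do not define a between-round endpoint. The minutes are maxima at the stated time limits or totals at the ideal times. A trainee who finishes Task 4 early gives a shorter continuous recording.

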The task will be set up by the facilitator and will give the trainee standardised instructions and a short demo video on how to perform this task (**Appendix 7**). The task begins when the trainee inserts the camera to find the character on the first target (e.g. **1**), zoom in and identify the small size character (e.g. **a**) located next to it. Before they can proceed to the next target, the facilitator needs to confirm that they are happy with the identification and placement of the small character by saying "next". Trainee can demonstrate this by placing the target in the circle on the screen and reading it out. Trainee can then navigate the camera to find the next target on the LASTT model which in the above example will be large character '**A**', then zoom in to find the small character next to it, put the small character in the circle on the screen and read it out. They can then move on when indicated by faculty as ok to do so. Trainee can then continue until they find the 14th target "**N end**" which completes the task. Please see figure 1 for an example. The facilitator will record the trainee's study number (badge number) and time taken to identify 14 targets. A time of 2 minutes and 30 seconds is considered as ideal for completion of this task. If trainee exceed this time then it will incur a penalty. For every

30 seconds they exceed beyond 2 minutes and 30 seconds, 1 target will be subtracted from the total number of targets they have found. The penalty column does not need to be completed at the time of assessment and can be worked out retrospectively. Furthermore maximum time allowed for this task is 5 minutes and if all 14 targets have not been identified within 5 minutes then the trainee is encouraged to move on to the second sequence of this task, i.e. round 2. The assessor will be required to record the last target found on the evaluation sheet if 5 minutes limit is reached and the task is still incomplete. The rationale for the 5 minute cap is to minimise fatigue. This task will be repeated 3 times and above data will be recorded on the evaluation sheet (**Appendix 8**). To avoid memory effect the sequence of targets will be changed each round so that there are 3 different sequences to find. The same 3 sequences will be used for all trainees throughout the testing phase (**please see the end of appendix 7**).

Task 2 - Hand eye co-ordination (HEC)

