- Task 1 is ideally completed in 2 minutes and 30 seconds, however trainees will not be confined to this time and will be allowed to continue until all 14 targets have been identified or reached 5 minutes. The rationale for putting a time limit of 5 minutes per round is to avoid fatigue. We will record the time taken (in minutes and seconds) to locate the 14 targets and will average this across 3 rounds. If the task is incomplete by 5 minutes, we will record the last found target (small character). Those trainees who are able to complete the task but have taken longer than 2 minutes and 30 seconds will incur a penalty. For every 30 seconds exceeded beyond 2 minutes and 30 seconds we will subtract 1 target from the total number of targets they have found.
- For tasks 2-3, we will record the time taken in minutes and seconds to complete the tasks and use an average of this across 3 rounds. If the tasks are not completed within time (i.e. 3 minutes) then we will record the number of objects handled within 3 minutes and take an average of this across 3 rounds. Where participant shows mixed/inconsistent performance (i.e. completes the task once in time (i.e. 3 minutes) but not on the other two runs then we will use the average number of handled objects over 3 runs and note the performance as mixed/inconsistent. If an object is dropped whilst being handled, the number of drops will be recorded as this indicates inefficient performance.
- For task 4 the number of sutures, correct knots and extent of trauma will be recorded on the evaluation sheet and maximum time allowed will be 15 minutes.

Secondary outcome measures:

- EMG and EEG signal analysis.
- Qualitative measures such as consultant's perception of trainee's laparoscopic ability and the abilities they regard as important at CCT using a likert scale of 1-5.

Regulatory issues

Consent

The research team responsible for conducting the study are trained medical practitioners and are able to assess capacity and take informed consent.

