Grasp the plastic head of the pin with Johan forceps using your non-dominant hand and lift the pin up.

Whilst elevated, pass the pin to the dominant hand by grasping the metal part of the pin with a Maryland grasper.

Place the pin (head or tail) in the corresponding coloured disc and repeat for all colours. Once the pin is positioned in the disc of the same colour, you may move on to the next coloured push pin. It is not necessary to position the entire length of the pushpin in the respective circle. You may use both hands to stop the pin from falling out.

You are only required to place 6 pins in their respective circles, i.e. one of each colour. If the pin is dropped, use the second pin of the same colour or you may re-grasp the fallen pin, as long as you can find the pin within the endoscopic boundaries.

This task will be repeated 3 times with 3 different colour sequences.

Exercise 4: Suturing and knot tying

The aim of this task is to perform 4 interrupted stitches using correct needle handling and intra-corporeal knot tying techniques.

Perform 4 interrupted sutures by taking a needle bite through the black dots in a horizontal plane. Please use the first 4 rows for your sutures and leave the 5th row.

Pass the suture by entering and exiting precisely within the black dots.

Perform an intra-corporeal knot with 3 throws. Ensure that the knot is secure.

Cut the excess suture using laparoscopic scissors leaving behind a tail of approx. 1-2cm.

[figure not shown]
The link to the video demonstration for tasks 1-3 is:

<https://europeanacademy.org/training-tools/lastt/>

[figure not shown]
The link to suturing demonstration video is:

<https://www.youtube.com/watch?v=2qCBvbWBJ64>

[figure not shown]
Below are the 3 different sequences to be used in task 1.

Sequence 1

Sequence 2

Sequence 3

The following are 3 different colour sequences to be used in task 2 and 3.

Colour sequence 1 for tasks 2 and 3

Colour sequence 2 for tasks 2 and 3

Colour sequence 3 for tasks 2 and 3.

Appendix 8

Task evaluation sheets for laparoscopic tasks

Please indicate the time as you read it on the stopwatch in MM:SS:HH

Task 1: Laparoscopic Camera Navigation (LCN)

Runs	Time required for identifying all 14 targets. (If within or up to 5 minutes taken).	If 5 minutes are exceeded, record the last found target (small character).	Penalties. To be filled after study tasks are completed.
1	: :		
2	: :		
3	: :		

Task 2: Hand- Eye Co-ordination (HEC)

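### The Task 1 penalty, part of the primary outcome, is stated in conflicting ways, so the same round can score up to 5 targets apart

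*Protocol*

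**What the plan says.** Three places in the protocol state the Task 1 penalty.

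- **Table 1 (Study Protocol, Part 2):** "Penalty- subtracting 1 target from the total found targets if ideal time of 2:30 is exceeded". This is one target in total, with no scaling by time and no condition that the round be finished.
- **Task 1 – Laparoscopic Camera Navigation:** "If trainee exceed this time then it will incur a penalty". For each 30 seconds beyond 2:30, "1 target will be subtracted from the total number of targets they have found". There is no condition that the round be finished. The section adds that the penalty can be worked out afterwards.
- **Outcome measures, primary outcome:** "If the task is incomplete by 5 minutes, we will record the last found target (small character"). The next sentence reads "Those trainees who are able to complete the task but have taken longer than 2 minutes and 30 seconds will incur a penalty", and the one after it gives the same rate of one target per 30 seconds.

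Two further places concern the recording of Task 1 but state no penalty rule. The Appendix 8 sheet says "If 5 minutes are exceeded, record the last found target (small character") and has an empty penalties column to be completed after the tasks. The assessor instructions in Appendix 13 say "then stop the trainee at that point and record the last target they found" and do not mention a penalty.

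**The concern.** There are two disagreements and one gap.

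1. **Rate.** Table 1 gives a flat one-target penalty. The other two places give a penalty that grows to five targets at the 5-minute cap.
2. **Who is penalised.** The Task 1 description covers anyone over 2:30. The primary outcome section ties the penalty to trainees who finish and, for unfinished rounds, mentions only recording the last target. It does not expressly exempt them, but its wording allows that reading.
3. **Part-blocks.** Nowhere is it said whether part of a 30-second block counts.

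Task 1 is a component of the primary outcome. Because the penalty is calculated after testing, the written rule alone fixes the score. Two analysts following different sections would score the same round differently. On the literal primary outcome wording, a trainee who fails to finish can outrank one who finishes. Choosing between the rules once the data are in would also invite the charge that the choice followed the results.

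**Working it through.** The protocol gives no figure to reproduce here, so the check applies each stated rule to the same rounds.

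**Inputs from the protocol:** 14 targets; ideal time 2:30 (150 s); cap 5:00 (300 s); the penalty wordings above.

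**Formulas**, with *t* the time in seconds and *f* the targets found, for *t* > 150:

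- Table 1: *f* − 1
- Task 1 description: *f* − (*t* − 150)/30, counting full blocks
- Primary outcome, read literally: the same if *f* = 14, otherwise *f*

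At the cap the per-block penalty is (300 − 150)/30 = 5 targets.

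| Round | Table 1 | Task 1 description | Primary outcome, literal |
|---|---|---|---|
| Finished at 3:00 | 13 | 13 | 13 |
| Finished at 3:30 | 13 | 12 | 12 |
| Finished at 4:00 | 13 | 11 | 11 |
| Finished at 5:00 | 13 | 9 | 9 |
| Stopped at 5:00, 13 found | 12 | 8 | 13 |
| Stopped at 5:00, 10 found | 9 | 5 | 10 |

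With full blocks, Table 1 differs from the per-block rule by 1 to 4 targets for every finished round of 3:30 or longer. On the literal primary outcome reading, an unfinished round with 13 targets beats every finish from 3:30 to 5:00 (12 down to 9). If part-blocks count, it beats every finish slower than 3:00. Part-block counting alone moves a finisher by one target: 2:45 scores 14 or 13.

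**How often the order reverses.** The protocol gives no round times, so these are assumptions: lognormal times, targets found at a constant rate, 5-minute cap, full blocks, 400,000 simulated pairs of rounds per setting. The share of all pairs in which the slower round scores higher on the literal primary outcome reading is:

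| Median round time (s) | 150 | 175 | 200 | 250 | 300 |
|---|---|---|---|---|---|
| Log-SD 0.36 | 0.4% | 1.6% | 3.9% | 9.4% | 11.4% |

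Over the same medians the range is 0.03% to 20% at log-SD 0.25 and 1.1% to 6.3% at log-SD 0.50. Table 1 and the Task 1 description give 0% throughout.

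**Effect on a group comparison.** The score is the mean of three rounds, for two groups with medians 20% apart. The assumptions are between-subject SD 0.30 and within-subject SD 0.20 on the log scale, 200,000 trainees per group and full blocks.

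| Medians (s) | Gap, Task 1 description | Gap, primary outcome literal | Reduction |
|---|---|---|---|
| 150 vs 180 | 0.74 | 0.48 | 1 − 0.48/0.74 = 35% |
| 200 vs 240 | 1.36 | 0.67 | 1 − 0.67/1.36 = 51% |
| 250 vs 300 | 1.75 | 0.77 | 1 − 0.77/1.75 = 56% |
| 300 vs 360 | 1.88 | 0.91 | 1 − 0.91/1.88 = 52% |

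The standardised gap is 0.46 to 0.56 under the Task 1 description and 0.49 to 0.52 on the literal primary outcome reading. The faster group stays ahead in every case.

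**The case against.** **The rate conflict nearly resolves itself.** Table 1 is introduced as a summary, and the two fuller sections agree on one target per 30 seconds. That shows which text is the outlier. But Table 1 states a complete, different rule under the heading of data to be recorded, so it still needs correcting.

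**The unfinished-round point is an inference.** The last sentence on the penalty in the primary outcome section carries no completion condition. It subtracts from the number of targets found, a phrase that does most work if fewer than 14 can be found. Reading it in line with the Task 1 description is therefore natural, and the reversal appears only on the other reading. This is fair: the wording permits the exemption but does not declare it. Two careful readers can still end up 5 targets apart.

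**The consequences are modest.** The smaller raw gap largely reflects a compressed scale, and the high reversal shares need many unfinished rounds (about 30% at a median of 250 s and 50% at 300 s, with log-SD 0.36). Completion time is also recorded and is untouched by the penalty, and the protocol does not say which measure is compared between groups. All of this stands and limits the severity.

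**A separate analysis plan could settle the scoring.** It could choose a rule, and part-blocks are a detail it might cover. The protocol would still contradict itself.

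**A full penalty can produce a negative score** (4 found at 5:00 gives 4 − 5 = −1). This is true, but such a score still ranks rounds in the right order.

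**Conclusion.** The concern holds and should be fixed. The conflict over the rate is explicit and worth up to 4 targets for a finished round (13 against 9 at 5:00). The conflict over unfinished rounds rests on a literal but available reading. It is worth 5 targets (13 against 8 for 13 targets found at 5:00), and on that reading some non-finishers rank above finishers. These scores follow directly from the protocol's own figures, counting full blocks.

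The reversal shares and group gaps depend on assumed round times and show the possible size only. They do not show that the study's conclusion would change.

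**What to change.** Use one rule in all three places.

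- **Primary outcome section:** drop the restriction to trainees who finish. For example: trainees who exceed 2 minutes and 30 seconds, whether or not they find all 14 targets by 5 minutes, will incur a penalty. A round stopped at 5:00 then carries the full 5-target penalty (150 s / 30 s).
- **Table 1:** change the flat penalty to one target for every 30 seconds beyond 2:30.
- **Task 1 description:** state that unfinished rounds are included.
- **Part-blocks:** say once whether they count, and refer to that statement elsewhere.

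Mean completion time over the three rounds can stay as stated. The cost is wording in three places. No new data are needed, because the time and last target are already on the Appendix 8 sheet and the penalty is calculated afterwards. The change should be made before any scores are calculated.
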